## 11- Toxicity and adverse events management

---

### Definition

An Adverse Event (AE) is defined as "Any untoward medical occurrence in a patient or clinical investigation subject administered an investigational product or therapy and which does not necessarily have a causal relationship with this treatment/therapy". An AE can therefore be any unfavorable and unintended sign (for example: an abnormal laboratory

finding), symptom, disease, or worsening of a pre-existing medical condition temporally associated with the use of an investigational product/therapy, whether or not considered related to the investigational product/therapy.

An AE related to the investigational product or therapy is also called an adverse reaction or side effect.

## Collection and Reporting

Every AE occurring during the clinical trial should be recorded on the corresponding page of the Case Report Form. Every AE should be documented, monitored and followed until the AE is recovered or until 12 months (3 years for radiation-induced fibrosis) after the intra-operative radiotherapy.

## Severity Criteria

The severity criteria should not be mistaken with the seriousness criteria which determine the conditions of notification. The severity or grade of adverse events is evaluated by the Investigator following the NCI-CTCAE classification version 4.0.

The CTCAE displays Grades 1 through 5 with unique clinical descriptions of severity for each AE based on this general guideline:

Grade 1 = Mild; asymptomatic or mild symptoms; clinical or diagnostic observations only; intervention not indicated.

Grade 2 = Moderate; minimal, local or noninvasive intervention indicated; limiting age-appropriate instrumental ADL (Any Day Life)\*.

Grade 3 = Severe or medically significant but not immediately life-threatening; hospitalization or prolongation of hospitalization indicated; disabling; limiting self-care ADL\*\*.

Grade 4 = Life-threatening consequences; urgent intervention indicated.

Grade 5 = Death related to AE.

\*Instrumental ADL refer to preparing meals, shopping for groceries or clothes, using the telephone, managing money, etc.

\*\*Self-care ADL refer to bathing, dressing and undressing, feeding self, using the toilet, taking medications, and not bedridden.

## Side effects of Special Interest: Radiation-induced Fibrosis

All cases of radiation-induced toxicities should be monitored closely. A radiation-induced side effect of special interest is radiation-induced fibrosis.

Acute toxicities could be observed during and after IORT:

- Hematoma
- Lymphorrhoea (punctures > 2).
- Breast infection
- Erythema.

Delayed toxicities after IORT (> 6 months):

- Fibrosis
- Telangiectasia.
- Breast Pain
- Hyperpigmentation
- Cutaneous atrophy.

The cases of radiation-induced toxicities will be recorded in the source documents and on the Case Report Form at 15 days, 3, 6, 12, 24 months then yearly during 3 years after the IORT. They will be evaluated according to the NCI-CTCAE classification version 4.0.

## Serious Adverse Events

A Serious Adverse Event (SAE) is an adverse event which:

- results in death
- is life-threatening
- requires in-patient hospitalization (>24h) or prolongation of existing hospitalization,
- results in persistent or significant disability or incapacity
- is a congenital anomaly/birth defect, or
- medically relevant

Life-threatening in this context refers to an event in which the patient was at risk of death at the time of the event; it does not refer to a reaction that hypothetically might have caused death if more severe.

A hospitalization scheduled by the protocol (biopsy, chemotherapy...) is not considered a SAE. A hospitalization or prolongation of hospitalization for technical, practical, or social reasons, in absence of an AE is not considered a SAE. A hospitalization planned prior to patient enrolment is not considered a SAE, provided that his occurrence/outcome is clearly not aggravated by the investigational product or therapy. A hospitalization < 24 hours is not considered a SAE, provided that the AE does not meet any other seriousness criteria.

The terms "disability" and "incapacity" match with all physical/psychological temporary or permanent handicaps, clinically significant with consequences for the physical or mental functioning and/or the quality of life of the patient.

Medical and scientific judgment should be exercised in deciding whether other situations should be considered serious events, such as important medical events that might not be immediately life-threatening or result in death or hospitalization but might put at risk the patient or might require intervention to prevent one of the other outcomes listed above. Such events are considered serious with seriousness criterion "medically relevant". Examples of such events are allergic bronchospasm, torsade de pointes or convulsions.

The EudraVigilance Expert Working Group (EV-EWG) has co-ordinated the development of an Important Medical Event Terms (IME) list, which could help Investigators to determine whether an AE is serious or not:

<http://eudravigilance.ema.europa.eu/human/textforIME.asp>

The IME list is intended for guidance purposes only, and is not a mandatory requirement for seriousness assessment and regulatory reporting. Other examples of serious adverse events with seriousness criterion "medically relevant" are second primary malignancies and any suspected transmission via a medicinal product of an infectious agent. For every SAE the Investigator and the Sponsor evaluate separately the possible causal relationship to the investigational product or therapy. These evaluations might be different one from the other (for example: in the Investigator's opinion the SAE is not related to the investigational product/therapy and in the Sponsor's opinion the SAE is related to the investigational product/therapy).

## SAE Notification Procedure

Every SAE occurring during the study period (from the signature of the informed consent form until up to 12 months after the intra-operative radiotherapy) should be notified to the Sponsor without any further delay, and within 24 working hours in all cases, using the "Serious Adverse Event Notification Form". This form should be completed following the completion instructions and be faxed to the Clinical Research Pharmacovigilance Unit of the ICM.

[name]  
[[contact]](mailto:[contact])  
[contact] / [contact]  
ICM - Clinical Research Pharmacovigilance Unit  
[name]

Every SAE occurring beyond the 12-month period following intra-operative radiotherapy, judged by the Investigator to be related to this radiotherapy, should also be notified to the Sponsor in the same conditions as every other SAE. The "Serious Adverse Event Notification Form" should be completed in English and only one diagnosis or one symptom (except for linked symptoms) should be reported to enable MedDRA coding. If several symptoms are documented in the source documents, only the main symptom will be reported as verbatim on the notification form.

After the initial notification, a follow-up report should be completed and faxed every time complementary information on the SAE becomes available. Finally, when the case is closed, a final report with the complete information should be completed and faxed to the Pharmacovigilance Unit ([contact]). Complementary information or clarification could be requested by the Sponsor using Data Clarification Forms (DCFs). The Sponsor could also ask the site to send the anonymized medical records or laboratory findings corresponding to the SAE.

The risk-benefit balance of the study is evaluated continuously by the Clinical Research Pharmacovigilance Unit of the ICM and this risk-benefit balance will be discussed in the periodic safety reports. These reports will contain all required regulatory aspects and will be submitted to the competent authorities.

### **Trial Discontinuation**

- Individual withdrawal :
- Withdrawal of informed consent
- Insufficiency skin-surface or unfavourable geometry
- Each withdrawal must be documented
- Investigator withdrawal

Scientific/Steering committee is allowed to close the study ahead of schedule (e.g. Insufficient recruitment, unexpected high toxicity, Ethical and medical considerations...).

## **12- Patient screening, inclusion and registration procedures**

The assessments required as part of screening can be completed in one or more visits. Signed informed consent prior to any study related procedure is required. Enrolment in the study is defined as both the signing of the Informed Consent and validation of eligibility by the investigator. The inclusion and exclusion criteria should be checked during the screening period to ensure appropriate subjects are assigned to receive study treatment.

Registration is performed at the Biostatistics Unit of ICM (Montpellier, France). Investigators can use a dedicated registration form inserted into the CRF and fax the filled and signed form to:

Biostatistics Unit - ICM

From Monday to Friday (9.00 AM to 5.00 PM)

[contact]

[contact]

The investigator will automatically receive a notification form by fax with the patient's identification number to be reported on each CRF page.

## 13- Independent Data Monitoring Committee (IDMC)

---

The IDMC has an advisory role and provides his opinion concerning all safety issues related to the study or the study treatment to the Sponsor and the Coordinating/Principal Investigator of the study, and to the competent authorities (CPP and ANSM). If applicable, they can also provide their opinion about the efficacy data of the study. The IDMC can advise the Sponsor to continue, modify or stop the study. The Committee Members must be experts in clinical research and/or the study indication. They should not be implicated in the study protocol (no Principal or Co-Investigators) and are not allowed to have financial interests in the study. The Committee Members should sign a Financial Disclosure Form and a Confidentiality Agreement before attending the IDMC.

In this study, the IDMC will be constituted by 3 experts: a radiotherapist, a surgeon and a methodologist. The Committee Members will meet at the scheduled time point corresponding at the 12 months follow-up of the first 25 included patients.

The IDMC will meet to review safety of the therapeutic strategy, in term of toxicity and oncologic events (local and systemic), and other issues related to the appropriate conduct of the trial.

The IDMC will be regularly informed of the occurrence of death from cancer according to the a priori early stopping rule.

The data will be provided to the IDMC members by the Sponsors Biostatistics Unit, and / or the Clinical Research Pharmacovigilance Unit, and / or the Study Coordinator. The Sponsor can ask the IDMC for an ad hoc advice beyond the scheduled time points.

The ICM's Independent Data Monitoring Committee Charter is provided in Appendix 15.

## 14- Statistical considerations

---

### 14.1. Sample size calculation

The primary objective is to evaluate the success rate at 12 months, defined as the non-observation of fibrosis at 12 months after IORT.

A success rate of 95% is expected. The sample size calculation is based on:

- The Fleming one-stage design with one-sided alpha=0.05 and beta=0.05.

- $p_0 = 80\%$  (success rate at 12 months, threshold below which we will consider the Intraoperative Radiotherapy toxicity as unacceptable, assuming 20% failure)
- $p_1 = 95\%$  (success rate target at 12 months)

A total of 46 evaluable patients are required; taking into account non-evaluable patients (postoperative histological results that do not meet the inclusion criteria or less than 3 assessments before 12 months), the number of subjects is adjusted to 65.

It should be noted that the alpha level is set at 5% (one-sided), risk of concluding as to efficacy ( $p > p_0$ ) whereas there is no efficacy ( $p \leq p_0$ ), and the beta level is set at 5%, risk of concluding as to the absence of efficacy ( $p < p_1$ ) whereas there is noteworthy efficacy ( $p \geq p_1$ ).

After inclusion of 46 evaluable patients, it will be possible to conclude that the study arm demonstrates inefficacy if the success number is less than or equal to 40, or efficacy if the success number is greater than or equal to 41.

The sample size and the decision rule are presented here-below:

Hyp.	Rate of success at 12 months	$p_0$	$p_1$	Fleming one-stage design *	N total
Rate		80	95	(46, $\leq 40$ , $\geq 41$ )	65

\* (N,  $n_1$ ,  $n_2$ )

N = total sample size required.

$n_1$  = maximal number of success required to conclude => non-efficacy.

$n_2$  = minimal number of success required to conclude => efficacy.

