Assessment criteria	
Primary criterion:
 
 
- grade <math>\geq</math> 2 late fibrosis, according to the NCI CTCAE v4.0 grading scale, occurring within 12 months following the IORT.
 
 
Secondary criteria:
 
Definitive cosmetic results:
 
 
- assessed by a physician and the patient
 
- Pictures will be taken before treatment, after 15 days, three, six, and twelve months then 1fs / year up to five years.
 
 
Toxicities Evaluation :
 
 
- assessed by a physician
 
 
Quality of life:
 
 
- assessed by a patient
 
- EORTC QLQ-C30, QLQ-BR23 questionnaires delivered before treatment, and after 15 days, three, six, twelve months and twenty-four months.
 
 
Local relapse-free survival (L-RFS):
 
 
- L-RFS is defined as the time from surgery with IORT to any ipsilateral breast tumor recurrence, or death, whichever occurs first.
 
 
Metastasis Relapse-free survival (M-RFS):
 
 
- M-RFS is defined as the time from the surgery with IORT to any metastatic disease (excluding the ipsilateral breast, contralateral breast, regional lymph nodes), or death, whichever occurs first.
 
 
Disease-free survival (DFS):
 
 
- DFS is defined as the time from the surgery with IORT to any recurrence, including local recurrence, metastasis, appearance of a
 

	
second primary tumor, or death from any cause, whichever occurs first.
 
Overall survival (OS):
 
 
- OS is defined as the time from surgery with IORT to death from any cause.
 
 
Mastectomy-free interval:
 
 
- MFI is defined as the time from the surgery with IORT to a mastectomy for any reasons (all other events will be ignored). All patients without mastectomy will be censored at last follow-up.
 

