STATISTICAL CONSIDERATIONS	
Sample size calculation
 
The primary endpoint is the success rate at 12 months, the success being defined as no grade <math>\geq 2</math> fibrosis according to NCI-CTCAE V4.0 classification.
 
A success rate of 95% is expected. The sample size calculation is based on:
 
 
• The Fleming one-stage design with one-sided alpha=0.05 and beta=0.05.
 
• <math>p_0 = 80\%</math> (success rate at 12 months, threshold below which we will consider the Intraoperative Radiotherapy toxicity as unacceptable, assuming 20% failure)
 
• <math>p_1 = 95\%</math> (success rate target at 12 months)
 
 
A total of 46 evaluable patients is required; taking into account un-evaluable patients, the number of subjects is adjusted to 65
 
It should be noted that the alpha level is set at 5% (one-sided), risk of concluding as to efficacy (<math>p > p_0</math>) whereas there is no efficacy (<math>p \leq p_0</math>), and the beta level is set at 5%, risk of concluding as to the absence of efficacy (<math>p < p_1</math>) whereas there is noteworthy efficacy (<math>p \geq p_1</math>)
 
After inclusion of 46 evaluable patients (at least 3 assessments within 12 months), it will be possible to conclude that the study demonstrates inefficacy if the success number is less than or equal to 40, or efficacy if the success number is greater than or equal to 41.
 
The patient size and the decision rule are presented here-below:
 
  
 Hyp	Rate of success at 12 months	<math>p_0</math>	<math>p_1</math>	Fleming one stage design*	N total	
   
 Rate		80	95	(46, <math>\leq 40</math>, <math>\geq 41</math>)	65	
  
 
*(N, n1, n2)
	Hyp	Rate of success at 12 months	$p_0$	$p_1$	Fleming one stage design*	N total	Rate		80	95	(46, $\leq 40$ , $\geq 41$ )	65
Hyp	Rate of success at 12 months	$p_0$	$p_1$	Fleming one stage design*	N total								
Rate		80	95	(46, $\leq 40$ , $\geq 41$ )	65								

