### **The study is planned to enroll 65 patients.**

The patient must provide a signed informed consent form prior to any study related procedure. The principal measured outcome will be the cutaneous fibrosis rate 12 months after treatment. We considered that a rate of 20% or more of Grade  $\geq 2$  fibrosis would be unacceptable.

All patients will be followed for:

- Survival and local breast control after this study treatment for an extended carcinologic follow-up.

- Toxicities during and after treatment (3, 6, 12 and 24 months after IORT and each year during 3 years)
- Survival follow-up will be done every 3, 6, 12 and 24 months after IORT and each year during 5 years by clinical visits unless death lost to follow-up or withdrawal of consent.

The survival follow-up period will continue for 3 years after the last patient was included in the study.

The end of study (last patient last visit) will occur after all patients have completed their last assessment.

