## 9-Primary endpoint

The fibrosis grade will be scored following the NCI CTCAE scale v4.0 at 12 months after the IORT (73).

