### 14.3. Statistical analysis

Statistical analyses will be detailed in the statistical analysis plan developed before the database is frozen.

Baseline characteristics, compliance to treatment, safety, and carcinologic events will be described.

Qualitative data will be described by frequencies and percentages and associated 95% confidence interval.

Continuous parameters will be described by mean, standard deviation, median and range.

The primary endpoint will be described by the percentage of patients without fibrosis at 12 months and its 95% confidence interval.

For secondary endpoints, EORTC QLQ-C30 and QLQ-BR23 will be described according to EORTC scoring manual at baseline and for each visit.

Time to event endpoints (L-RFS, M-RFS, DFS, OS and mastectomy-free interval) will be estimated using Kaplan-Meier method and described by their rates and 95% confidence intervals at 12 months, 24 months, and 3 years.

Statistical analyses will be performed with STATA software v13 (Stata Corporation, College Station, TX, USA).

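### Sections 14.1 and 14.3 drop the grade ≥2 threshold from the primary endpoint, so read literally grade 1 fibrosis counts as failure against limits set for grade ≥2

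*Protocol*

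**What the plan says.** The protocol defines success on the primary endpoint in two ways.

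**With a grade threshold**
- Synopsis, assessment criteria: the primary criterion is grade ≥2 "late fibrosis, according to the NCI CTCAE v4.0 grading scale, occurring within 12 months following the IORT".
- Synopsis, statistical considerations: "The primary endpoint is the success rate at 12 months, the success being defined as no grade", followed by ≥2 fibrosis under CTCAE v4.0. This stands directly above p0 = 80% and p1 = 95%.
- Section 6: "We considered that a rate of 20% or more of Grade" ≥2 fibrosis would be unacceptable. This corresponds to the 20% failure behind p0.

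**Without a grade threshold**
- Section 14.1: "The primary objective is to evaluate the success rate at 12 months, defined as the non-observation of fibrosis at 12 months after IORT". The same p0, p1, 46 evaluable patients and pass mark of 41 follow.
- Section 14.3: "The primary endpoint will be described by the percentage of patients without fibrosis at 12 months and its 95% confidence interval".

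Section 9, the primary endpoint section, does not settle the matter: "The fibrosis grade will be scored following the NCI CTCAE scale v4.0 at 12 months after the IORT". It requires grading but names no cut-off.

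Two smaller differences accompany this. The first synopsis entry counts fibrosis occurring within 12 months, whereas the synopsis statistics and Sections 9, 14.1 and 14.3 refer to status at 12 months. Section 6 alone restricts the outcome to the skin: "The principal measured outcome will be the cutaneous fibrosis rate 12 months after treatment".

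**The concern.** The protocol's general severity scale (Section 11) treats grade 1 as a separate, mild category needing no intervention. Absence of fibrosis and absence of grade ≥2 fibrosis therefore classify some patients differently. The limits of 80% and 95% were justified for grade ≥2, yet the statistical section attaches them to an endpoint that, as worded, also counts grade 1 as failure. Nothing in Sections 9 or 14 restores the threshold or refers back to the synopsis.

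The go/no-go conclusion of a single-arm trial is at stake. A treatment that meets its grade ≥2 target could be declared unacceptable. Section 14.3 also leaves the analysis plan to be written at any time before database freeze, so someone could choose between two definitions, each supported by the protocol, after outcomes have accrued.

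**Working it through.** **Inputs** (synopsis and Section 14.1): p0 = 0.80, p1 = 0.95, one-sided alpha = 0.05, beta = 0.05, Fleming one-stage design, N = 46 evaluable, positive conclusion at 41 or more successes, negative at 40 or fewer. The rule therefore tolerates 46 − 41 = 5 failures.

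**Step 1: reproduce the plan's sample size.** Normal approximation:

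n = [(z₀.₉₅·√(p0(1−p0)) + z₀.₉₅·√(p1(1−p1))) / (p1−p0)]²

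= [(1.645 × 0.4000 + 1.645 × 0.2179) / 0.15]² = 45.92, rounded up to 46.

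The stated 46 is reproduced. With X ~ Bin(46, 0.95), the exact probability that X ≥ 41 is 97.4%, so power at the target exceeds the planned 95% when success means no grade ≥2 fibrosis. (At p = 0.80 the exact probability of passing is 7.98%, above the nominal 5%. That is a separate matter and plays no part here.)

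**Step 2: apply the Section 14 wording literally.** Hold true grade ≥2 fibrosis at the 5% design target and let g be the proportion of patients with grade 1 fibrosis. If grade 1 counts as failure, the success probability is p = 0.95 − g, and the chance of passing is P(X ≥ 41) with X ~ Bin(46, p). The protocol gives no value for g, so it is varied as an assumption.

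| Assumed grade 1 rate g | Success probability p | P(X ≥ 41 of 46) |
|---|---|---|
| 0% | 0.95 | 97.4% |
| 2% | 0.93 | 90.0% |
| 5% | 0.90 | 69.0% |
| 10% | 0.85 | 29.3% |
| 15% | 0.80 | 8.0% |
| 20% | 0.75 | 1.5% |

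At g = 15% the any-grade success rate equals p0, although the grade ≥2 target is met exactly.

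**Step 3: how much grade 1 fibrosis matters.**
- P(X ≥ 41) = 0.95 at p = 0.9416, so g = 0.95 − 0.9416 = 0.84%.
- P(X ≥ 41) = 0.50 at p = 0.8776, so g = 0.95 − 0.8776 = 7.2%.

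**Step 4: the same data under both definitions.** At a 5% rate, 46 × 0.05 = 2.3 grade ≥2 cases are expected. Take 2 grade ≥2 cases and 4 grade 1 cases.
- Synopsis definition: 46 − 2 = 44 successes. Since 44 ≥ 41, the trial passes.
- Section 14.1 as worded: 46 − 2 − 4 = 40 successes. Since 40 ≤ 40, the trial fails.

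**The case against.** The strongest reply is that the intention is clear. The synopsis states the grade ≥2 threshold twice, Section 6 bases the 20% limit on it, and Section 14.1 repeats that limit through p0. No passage argues for an any-grade endpoint, and requiring a grade in Section 9 would serve little purpose if every fibrosis were a failure. Dropped shorthand is the natural reading. The power loss needs an analyst who ignores the synopsis and Section 6, together with a grade 1 rate the protocol does not supply. The error is also conservative: counting grade 1 as failure can only make a positive conclusion harder, never pass an unacceptable grade ≥2 rate. And because grades are recorded at each visit, either version can be computed later.

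Most of this stands. The omission probably is shorthand, the sample size is not wrong, and the risk is a false negative. But the ungraded definition sits beside the decision rule and is repeated in the analysis section, and Section 9 does not correct it. Clear intent makes the correction uncontroversial; it does not remove the contradiction. A later analysis plan could confirm the threshold, but the protocol would still contradict itself on the event that decides the trial.

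On the time frame, the objection has more force. The synopsis speaks of late fibrosis, and Section 11 lists fibrosis under "Delayed toxicities after IORT (> 6 months"). The only scheduled visit after 6 months and up to 12 months is the 12-month visit, so the two wordings largely coincide on the planned schedule. That difference and the restriction to the skin are secondary, and no effect has been quantified for either.

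**Conclusion.** The concern holds. Sections 14.1 and 14.3 define and analyse primary success without the grade ≥2 threshold on which p0, p1 and the 41-of-46 rule were based, and Section 9 does not supply it. This is a contradiction within the protocol, not a detail that can be left to an analysis plan.

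If Section 14 is followed literally and grade ≥2 fibrosis is truly 5%, the chance of passing falls from 97.4% to 69.0% with 5% grade 1 fibrosis and to 29.3% with 10%. It drops below the planned 95% once grade 1 exceeds 0.84%. These figures assume independent patients, exactly 46 evaluable, and grade 1 rates chosen for illustration. That identical data can give opposite conclusions under the two definitions does not depend on any assumed rate.

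**What to change.** - **Section 14.1:** define success as no CTCAE v4.0 grade ≥2 fibrosis.
- **Section 14.3:** analyse the percentage of patients without grade ≥2 fibrosis, with the chosen time frame, and report any-grade fibrosis descriptively.
- **Section 9:** state the same threshold.
- **Secondary:** the sponsor should choose one time-frame wording, decide whether the restriction to cutaneous fibrosis applies, and use the result in the synopsis and Sections 6, 9, 14.1 and 14.3. The wording should fit the synopsis's reference to late fibrosis, the delayed-toxicity heading in Section 11 and the existing requirement in Section 14.4 for three assessments, without adding a new evaluability condition.

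The cost is protocol wording only. Section 11 already has radiation-induced toxicities recorded and graded at 15 days and at 3, 6 and 12 months, so no new data are needed. This correction changes neither N = 46, p0, p1 and the pass mark of 41 nor the evaluable population.

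### The success rule of 41 or more out of 46 carries an exact one-sided type I error of 8.0%, not the stated 5%; the cut-off is one success too low

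*Protocol*

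**What the plan says.** Section 14.1 of the protocol gives these design parameters:

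- Design and error rates: "The Fleming one-stage design with one-sided alpha=0.05 and beta=0.05".
- Null success rate p0 = 80%, described as the "threshold below which we will consider the Intraoperative Radiotherapy toxicity as unacceptable, assuming 20% failure".
- Target p1 = 95%: "A success rate of 95% is expected".
- Sample size: "A total of 46 evaluable patients are required", raised to 65 enrolled to allow for non-evaluable patients.
- Decision rule at 46 evaluable patients: "inefficacy if the success number is less than or equal to 40, or efficacy if the success number is greater than or equal to 41".

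Section 14.1 also defines its alpha: "the alpha level is set at 5% (one-sided), risk of concluding as to efficacy" when the true rate is at or below p0. The table in 14.1 repeats the rule as (46, ≤40, ≥41), and its footnote makes the last figure the smallest number of successes that allows a positive conclusion. The synopsis has the same rule in its text ("inefficacy if the success number is less than or equal to 40", "efficacy if the success number is greater than or equal to 41") and in its table. All four places agree, so this is neither a misprint in one of them nor a conversion fault.

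**The concern.** The protocol prints a numerical cut-off beside a numerical error rate, and the two do not belong together. Since alpha is defined as the chance of a positive conclusion when the success rate is no better than 80%, it can be checked directly against the binomial distribution.

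This is the only final decision rule for the primary endpoint, and that endpoint is tolerance. Section 6 treats grade ≥2 fibrosis in 20% or more of patients as unacceptable, which is the same boundary as p0. A cut-off that is too low therefore errs towards accepting toxicity that the protocol has declared unacceptable. A result of exactly 41/46 would be called a success although the matching one-sided 5% confidence bound does not exclude 80%.

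**Working it through.** **Inputs** (section 14.1): p0 = 0.80, p1 = 0.95, one-sided alpha = 0.05, beta = 0.05, so z = 1.645 for both; N = 46; success if X ≥ 41.

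**1. The plan's sample size.** The one-stage normal approximation is

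n = [(z·√(p0(1−p0)) + z·√(p1(1−p1))) / (p1−p0)]²

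= [1.645 × (√0.16 + √0.0475) / 0.15]² ≈ 45.92, rounded up to 46.

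The stated N is reproduced.

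**2. The cut-off under the same approximation.**

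n·p0 + z·√(n·p0(1−p0)) = 46 × 0.80 + 1.645 × √(46 × 0.80 × 0.20) = 36.8 + 1.645 × 2.713 = 41.26.

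Forty-one lies below this value, so the smallest count that rejects p0 is 42. The printed cut-off is one too low by the design's own formula.

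**3. Exact type I error of the printed rule.** With X ~ Binomial(46, 0.80):

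P(X ≥ 41) = 0.04664 + 0.02221 + 0.00826 + 0.00225 + 0.00040 + 0.00003 = 0.0798.

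The normal approximation for X ≥ 41 gives 6.1% without continuity correction, from (41 − 36.8)/2.713 = 1.55. With the correction it gives 8.6%, from (40.5 − 36.8)/2.713 = 1.36. No method tried gives 5% or less.

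**4. Neighbouring cut-offs and the smallest design that meets both rates** (exact binomial):

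| Evaluable N | Success if ≥ | Alpha at 80% | Power at 95% |
|---|---|---|---|
| 46 | 40 | 15.9% | 99.2% |
| 46 | 41 (printed) | 8.0% | 97.4% |
| 46 | 42 | 3.3% | 92.1% |
| 46 | 43 | 1.1% | 80.3% |
| 50 | 45 | 4.8% | 96.2% |

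At N = 46 no cut-off keeps both errors at or below 5%. An exact search upward in N finds 45/50 as the first design that does.

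**5. Confidence limits** (exact Clopper-Pearson; the two-sided 90% interval matches a one-sided 5% test):

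| Result | 90% lower limit | 95% lower limit |
|---|---|---|
| 41/46 (89.1%) | 78.5% | 76.4% |
| 42/46 (91.3%) | 81.2% | 79.2% |

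On the matching 90% interval, 41/46 does not exclude 80% and 42/46 does.

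**The case against.** The best case for leaving the rule alone is one of scale. The error is a single patient in a single-arm phase II feasibility trial. The excess is about three percentage points (8.0 − 5.0) and applies at a true success rate of exactly 80%. At 78% the printed rule accepts with probability 4.3%, and at 75% with probability 1.5%. Power is higher than stated (97.4% against 95%), so part of the effect is a trade between the two errors. Other safeguards exist as well: the independent committee reviews toxicity at 12 months of the first 25 patients (section 13), and the study can be suspended for a high fibrosis rate (section 6). This puts the size in proportion, but it does not make the stated alpha true, and none of those safeguards is a numerical rule for the primary endpoint. The numerical stopping rule in section 14.2 concerns cancer deaths.

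Three limits on the argument should be granted.

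- The 95% interval that section 14.3 plans to report is not evidence against the cut-off. Even at 42/46 its lower limit is 79.2%, because a two-sided 95% interval is stricter than a one-sided 5% test. Only the 90% interval separates 41 from 42.
- The protocol ties 41 to 46 evaluable patients and nowhere applies it to another number. If 41 were kept regardless, alpha would be 0.44 at 50 evaluable patients and 0.88 at 55, but no text says it would be. A cut-off for other counts could also be set in the analysis plan.
- Moving to 42/46 gives up the stated beta (7.9% instead of 5%), so the correction has a price.

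**Conclusion.** The point holds. The printed rule has an exact one-sided type I error of 7.98% against the stated 5%, with power 97.4% against the stated 95%. The fault lies in the cut-off and not in the sample-size formula, because N = 46 is reproduced and the same formula calls for 42. A later analysis plan would not cure it, since the protocol itself states both the rule and its error rates.

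The calculation assumes independent patients with a common success probability and exactly 46 evaluable patients. It does not depend on whether success is read as no fibrosis (section 14.1) or no grade ≥2 fibrosis (synopsis), because p0 is 80% in both. The excess is modest, but it concerns the final decision on the primary endpoint and errs towards accepting toxicity, so it should be corrected.

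**What to change.** In section 14.1 and the synopsis, text and tables, change the rule for 46 evaluable patients to failure at 41 or fewer and success at 42 or more. Restate the error rates as alpha 3.3% and power 92.1% (beta 7.9%).

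If the sponsor prefers to keep both stated rates, require 50 evaluable patients and success at 45 or more (alpha 4.8%, power 96.2%). With 65 enrolled, this lowers the allowance for non-evaluable patients from 29% (1 − 46/65) to 23% (1 − 50/65).

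In either case, add two sentences:

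- If the number of evaluable patients differs from the planned one, the cut-off is the smallest c with P(X ≥ c | n, 0.80) ≤ 0.05. Examples are 45/50, 50/55 and 54/60. This rule protects alpha but not always beta: at 50/55 power is 94.4%.
- The exact 90% confidence interval will be reported beside the 95% interval, so that one reported interval agrees with the one-sided 5% test.

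The cost is wording in two places and no extra patients. On the first route the stated power falls from 95% to 92%; on the second, the margin for non-evaluable patients shrinks. The change must be made before the primary results are known, because moving the cut-off after seeing exactly 41 successes would not be credible.
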